6 STUDY INTERVENTION

6.1 STUDY INTERVENTION(S) ADMINISTRATION

6.1.1 STUDY INTERVENTION DESCRIPTION

Study drugs will be provided and stored at 36-46°F in Neurosciences IDS pharmacy refrigerator.

- Estradiol 0.1mg topical patch, 4 patches/box
- Progesterone 100mg capsules, 100 capsules/bottle
- Placebo capsules, 100 capsules/bottle (Capsugel Orange, Size AA, DB Capsules)
- Placebo patches (provided by study)

6.1.2 DOSING AND ADMINISTRATION

Under double-blind procedures, women randomized to placebo-E2 will take placebo P4; those randomized to active E2 will take active P4.

By avoiding the first-pass metabolic effects of oral estrogen, transdermal E2 creates stable, premenopausal follicular phase E2 blood levels; and a physiologic profile of E2 relative to its metabolites estrone and estriol.³⁵⁻³⁷ Transdermal E2 also has a superior thromboembolic and metabolic safety profile than oral estrogen.³⁸⁻⁴⁰ A 7-day transdermal system provides significantly more stable concentrations and better patch adherence than twice weekly patches.⁴¹ We have chosen generic estradiol 7 day patches because the adhesive layer of the matrix distributes E2 molecules to continuously release E2, which is transported across skin leading to sustained levels of E2.³⁵ Because of the dynamic changes in the reproductive axis during the MT and the possibility that, over 24 weeks, some women may transition from one STRAW stage to another, placebo will control for effects of reproductive aging, *per se*, on measures of interest and for habituation effects to repeat testing.

Progesterone Administration: To reduce the risk of E2-induced endometrial hyperplasia, women randomized to active E2 will take 200 mg micronized progesterone/day x 12 days during weeks 17-18 (8 weeks after randomization) and again eight weeks later at the end of the study (weeks 25-26). Although in clinical settings progesterone tends to be given either every day or for 12 days once per month, the literature is inconclusive regarding the precise regimen that provides the best protection against endometrial hyperplasia or endometrial cancer.

We have chosen to give P4 in a discontinuous fashion instead of using a transdermal system that delivers both E2 and a progestin because progestins not only antagonize E2 effects^{43,44} but because the metabolites of progesterone (e.g., allopregnanolone) are potent modulators of the HPA axis response to stress. Thus, this would introduce a confound and mitigate against our ability to examine the role of E2 variability on the HPA axis stress response.

6.2 PREPARATION/HANDLING/STORAGE/ACCOUNTABILITY

6.2.1 ACQUISITION AND ACCOUNTABILITY

The study coordinator will notify the IDS Pharmacy of a patient's enrollment by the presentation of a pre-printed prescription. The prescription will contain the patient's name, medical record number, patient number, study visit week, informed consent, allergies, quantity of drug to be dispensed, date, and signature of an authorized prescriber. Dispensed study drugs are labeled with Vestigo outpatient prescription labels. All study drug returns may be discarded following documentation.

6.2.2 FORMULATION, APPEARANCE, PACKAGING, AND LABELING

Active: Alvogen brand estradiol 0.1mg topical patch and generic prometrium progesterone 100mg capsules

Control: Placebo patches supplied by PI. Placebo capsules from Capsugel, orange, size AA, DB.

All patches will be dispensed in individually wrapped packages without manufacturer branding. Pills will be contained in Capsugel capsules and active/control capsules will be identical in appearance.

6.2.3 PRODUCT STORAGE AND STABILITY

Drugs will be stored in the Neurosciences IDS Pharmacy refrigerator at 36-46°F.

6.2.4 PREPARATION

Addressed in 6.2.2 above.

6.3 MEASURES TO MINIMIZE BIAS: RANDOMIZATION AND BLINDING

Under double-blind procedures, subjects will be randomized to receive E2 or placebo for 16 weeks. The study biostatistician will create the randomization scheme and UNC Investigational Drug Services will manage the randomization and dispensing of hormones in blinded form. For those randomized to transdermal E2 (n=60), each will wear a patch delivering 0.10 mg E2/24. Those randomized to placebo (n=60), will wear a patch similar in appearance.

6.4 STUDY INTERVENTION COMPLIANCE

Compliance checks will occur at every study visit. Subjects will:

1. Be educated on the importance of replacing their patches every 7 days and we will develop an individualized behavior strategy to enhance compliance.
2. Record date of patch application, reviewed at each visit
3. Bring used an unused patches to each visit.
4. Be giving extra patches for replacement if necessary.

6.5 CONCOMITANT THERAPY

Not applicable

6.5.1 RESCUE MEDICINE

Not applicable.

7 STUDY INTERVENTION DISCONTINUATION AND PARTICIPANT DISCONTINUATION/WITHDRAWAL

7.1 DISCONTINUATION OF STUDY INTERVENTION

At six-month intervals, the Biostatistician on the study will test whether there are significant differences between those in the active E2 versus placebo E2 for moderate or severe AEs. The statistical analysis method will be a two-sided Fisher exact Test, with alpha = 0.05. These results will be provided to the Data Safety and Monitoring Board (DSMB) along with the summary report of enrollment and other safety data. The DSMB will consider stopping the study based on the results of the statistical tests and other safety data.

7.2 PARTICIPANT DISCONTINUATION/WITHDRAWAL FROM THE STUDY

1. In the case of mood deterioration, [name] (licensed clinical psychologist) will determine the next course of action, including a reassessment more frequently or more urgently if deemed to be clinically required. Participants will be withdrawn and referred for treatment to the UNC Center for Women's Mood Disorders if, in the opinion of [name] the mood disturbance warrants pharmacological or other intervention and is rated Grade III or higher.
2. Any participant with emergent suicide ideation with intent or suicide behaviors will be removed from the study. Based on the clinical assessment by [name], she will either be taken to the emergency room or referred for treatment.
3. Development of a VTE, breast carcinoma, Stage 2 hypertension, or other medical conditions for which E2 is contraindicated.
4. Development of endometrial hyperplasia.
5. Start of an exclusionary prescription medication or herbal supplement (e.g., psychotropics)
6. Failure or inability to comply with study procedures as determined by study staff and ultimately by [name].
7. For participants who report experiencing current migraines (with or without aura) at the initial enrollment, staff will incorporate additional protocol to monitor all headaches they experience throughout the study protocol. Staff will document this headache assessment during each weekly visit, both before and after randomization. Should a participant report experiencing migraine with aura prior to randomization, they will not be randomized and complete the baseline visits only. If a participant reports a migraine with aura post-randomization, they will discontinue use of HRT immediately and be withdrawn from the study. If a participant reports an increase in frequency or severity of migraine without aura post-randomization, they will be referred to [name] for further assessment.

7.3 LOST TO FOLLOW-UP

The following actions must be taken if a participant fails to return to the clinic for a required study visit:

- The site will attempt to contact the participant and reschedule the missed visit within 7 days and counsel the participant on the importance of maintaining the assigned visit schedule and ascertain if the participant wishes to and/or should continue in the study.
- Before a participant is deemed lost to follow-up, the investigator or designee will make every effort to regain contact with the participant. These contact attempts will be documented in the participant's medical record or study file.

- Should the participant continue to be unreachable, he or she will be considered to have withdrawn from the study with a primary reason of lost to follow-up.

8 STUDY ASSESSMENTS AND PROCEDURES

8.1 EFFICACY ASSESSMENTS

This is not a clinical efficacy trial.

8.2 SAFETY AND OTHER ASSESSMENTS

Safety Screening prior to randomization:

- **Physical examination:** height and weight will be measured to determine eligibility based on BMI. Gynecological exam by Investigator gynecologist will determine if subjects have any signs or history of endometrial disorder, abnormal uterine anatomy, or abnormal ovarian anatomy (confirmed by endometrial ultrasound and/or biopsy).
- **Vital signs** Three stethoscopic blood pressure readings will be measured at enrollment to rule out hypertension.
- **Radiographic assessments.** Subjects will be required to have normal results from a screening mammogram within 12 months prior to enrollment.

The Snaith-Hamilton Pleasure Scale (SHAPS): ¹⁰⁴ assesses anhedonia. SHAPS scores range from 14-56, with higher scores corresponding to higher levels of anhedonia. This scale has shown adequate overall psychometric properties in clinical and student samples ¹⁰⁵. The SHAPS has satisfactory test-retest validity in healthy participants (intraclass correlation coefficient = 0.70, p < 0.001 ¹⁰⁶).

The State-Trait Anxiety Inventory (STAI): the state measure of anxiety from the STAI consists of items such as "I am worried" or "I feel calm" and participants complete the items as to how they currently feel. A higher score indicates higher anxiety. While there are no standard clinical cut-offs for the STAI, past research indicates scores ≥ 40 are clinically significant. ^{107,108} The scale has good median alpha reliability (.92). ¹⁰⁹

Dot-probe (DP) task (15 min): will measure attentional bias to threat (threat responsivity)¹¹⁹. An angry and a neutral face of the same individual are presented vertically simultaneously (trials with neutral faces are controls). Immediately following the face pair, a probe letter replaces either the angry face (threat congruent trial) or the neutral face (threat incongruent trial). Participants indicate the probe letter via button press. The task consists of 144 trials (48 threat congruent, 48 threat incongruent, 48 neutral). Trials are separated by a variable length inter-stimulus interval (900 - 1300 ms). Bias scores are calculated by subtracting the reaction time on threat congruent from threat incongruent trials. Positive scores reflect a bias towards threat and negative scores reflect a bias away from threat. Attention bias calculations exclude trials with incorrect responses, trials with reaction times <150 ms or >2000 ms or >2.5 SD outside the mean.

Effort Expenditure for Rewards Task ("EEfRT") (20 min) will measure approach motivation that indexes the willingness to expend effort to obtain monetary rewards under varying conditions of reward probability and magnitude ¹²⁰. On each trial, participants choose between an "easy task" and a "hard

task" and are presented with information about the probability of winning (i.e., 12%, 50%, or 88%), and the magnitude of the potential reward if they complete the button-press task successfully (range:\$1.24 - \$4.12). Completion of the easy task requires 30 button presses in 7 seconds using the dominant index finger, whereas completion of the hard task requires 100 presses with the non-dominant "pinky" finger in 21 seconds. The % of hard task choices is the dependent measure. We have experience with this task in clinical studies of reward processing deficits ¹²¹.

The Trier Social Stress Test (TSST) involves social evaluation of speech and serial subtraction stress and induces large HPA axis responses 122-125. Baseline Rest (30 mins): The subject will rest for 30 minutes. Instructions: (5 min) Subjects are introduced to a 2-person committee. The subject will assume the role of a job applicant who is invited for a personnel interview with the committee. Anticipation: The subject prepares for 10 min. Speech: The committee asks the subject to deliver her talk for 5 mins. The committee responds with prepared questions to ensure that the talk lasts for 5 mins. Serial Subtraction: The subject is given a number to start from and asked to subtract a number from that original number as fast and as accurately as possible for 5 mins. For each mistake, the subject restarts at the original number. Stress Recovery: The subject rests alone for 45 mins. The characteristics of the TSST that elicit large HPA axis response include: 1) lack of controllability; 2) creation of a context of forced failure; and 3) social evaluative threat²⁸. Thus, the TSST provides a physiologic unit of analysis for the construct of threat responsivity. To minimize habituation, we will use the second TSST at baseline week 8 as the comparison for all analyses (the first TSST will be used to eliminate the novelty effect). Modifications with each TSST will minimize habituation:¹²⁶ 1) a different speech topic, such as modifying the job; describing one's positive and negative personality attributes and impact on likeability¹²⁶; 2) different numbers in the serial subtraction; 3) different, opposite sex committee members each time. With these modifications, some novelty is maintained even with repeat exposure, ensuring a significant HPA response.

Neuroendocrine Sampling during Stress Testing: Plasma cortisol will be taken at the end of baseline rest and again during Recovery at minutes 20, 30, and 45, wince HPA-axis reactivity is reliably seen 10-30 minutes after cessation of the TSST ^{22,26}.

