1.3 SCHEDULE OF ACTIVITIES (SOA)

Procedures	Medical Screening and Enrollment Week 0	Lab Session- Baseline Assessments & Randomization Week 8	Lab Session- Study Intervention, Side Effects, and Compliance Checks Week 16	Lab Session- Study Intervention, Side Effects, and Compliance Checks Week 20	Final Lab Session- Study Intervention, Side Effects, and Compliance Checks Week 24
Informed consent	X				
Demographics	X				
Medical history	X				
Physical and gynecological exam (including height and weight)	X				
Screening mammogram	X				
Pregnancy test ^a		X			
Randomization		X			
Administer transdermal estradiol/placebo		X	X	X	
Administer micronized progesterone/placebo			X		X
Discontinue transdermal estradiol/placebo					X
Administer STAI and SHAPS questionnaires		X	X	X	X
Administer Dot Probe and EEfRT behavioral tasks		X	X	X	X
Administer Trier Social Stress Test (TSST) and collect serum to measure cortisol ^b		X	X	X	X
Adverse event review and evaluation		X	X	X	X

a: urine pregnancy test (women of childbearing potential)
 b: serum collected at the end of baseline rest and at minutes 20, 30, and 45 of recovery post-TSST

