2.3 RISK/BENEFIT ASSESSMENT

2.3.1 KNOWN POTENTIAL RISKS

The most frequent side effects associated with estradiol use include:

- breast tenderness (occurs in 29% of patients)
- abdominal cramps (occurs in 16% of patients)
- headache (occurs in 13% of patients)
- edema (swelling) (occurs in 10% of patients)
- nausea (occurs in 6% of patients)
- depression, nervousness (occurs in 11% of patients)
- acne (occurs in 3 – 12% of patients)
- skin rash or irritation may also occur at site where the patch is placed (occurs in 3 - 12% of patients)

Less frequent side effects associated with estradiol use include:

- jaundice (yellowing of skin)

- increased blood pressure
- worsening of migraines or asthma
- enlargement of uterine fibroids
- intolerance to contact lenses
- dizziness
- changes in appetite and weight

The most common side effects associated with progesterone use include:

- breast tenderness (occurs in 16% of patients)
- dizziness (occurs in 24% of patients)
- abdominal cramping (occurs in 20% of patients)
- headache (occurs in 16% of patients)
- viral infection (occurs in 12% of patients)
- joint pain (occurs in 12% of patients)
- diarrhea (occurs in 8% of patients)
- menstrual bleeding, sometimes consistent with a heavy menstrual period (occurs in 20-30% of patients)
- drowsiness (occurs in 9% of patients)

Less common side effects associated with progesterone use include:

- vaginal discharge
- chest pain
- abdominal bloating

Rare yet Serious Risks Associated with Perimenopausal Hormone Use:

The Women's Health Initiative (WHI) study results will be summarized here to provide a context for understanding risk and the current expert opinions about hormone administration to women in the menopausal transition.

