5.2 EXCLUSION CRITERIA

An individual who meets any of the following criteria will be excluded from participation in this study:

1. Any history of CVD, including coronary artery disease, arteriosclerosis, heart attack, or stroke.
2. Type I or II diabetes
3. Stage I or greater hypertension based on 3 stethoscopic measures at enrollment.
4. Personal or family history suggesting elevated risk for E2-related cancer or thrombotic events.
5. Sensitivities to any ingredient in transdermal E2 or micronized P4
6. Use of psychotropics, statins, or hormonal preparations.
7. Use of herbal supplements that may affect mood or menopause symptoms (e.g., Black Cohosh or St. John's Wort)
8. Nicotine use of greater than 10 cigarettes per day.
9. BMI of greater than or equal to 36
10. History of migraine headaches in current smokers
11. History of migraine with aura within the last 3 years
12. History of psychotic disorders, bipolar disorder, or severe substance use disorder (within 10 years of enrollment)
13. History of suicide attempts, or current suicide ideation with intent
14. History gall bladder disease, liver dysfunction, or other disorders for which E2 or P4 is contraindicated
15. History or signs of endometrial disorder (based on gynecological exam)
16. Pregnancy or lactation
17. Known allergic reactions to components of the <study intervention>, <specify components/allergens>

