8.3.3 CLASSIFICATION OF AN ADVERSE EVENT

8.3.3.1 SEVERITY OF EVENT

The following guidelines will be used to describe severity of AEs.

- **Mild** – is defined as having no effect on activities of daily living such as transient light headedness or sweating with venipuncture; breast tenderness, mild skin irritation; or something of equal significance that requires no medical intervention and is of marginal clinical relevance.
- **Moderate** – would be associated with temporary (minutes to a few days) disruption in activities of daily living such as temporary loss of consciousness with venipuncture; a worsening of migraines or headache that require bed rest, an increase in anxiety or anhedonia symptoms consistent with clinically meaningful levels, emergent suicide intent without specific plan (severity level 4 on the C-SSRS), excess sleepiness or fatigue that resolves with additional rest, or something of equal significance.
- **Severe** – would cause serious disruption in daily activities of living and may or may not require hospitalization. Examples of such events would include a thromboembolic event, breast carcinoma, an increase in blood pressure consistent with Stage 2 hypertension, any cardiovascular event, any event that is permanently disabling, any event requiring hospitalization or is life threatening, severe mood impairment or emergent suicide ideation with specific plan (severity level 5 on the C-SSRS) or any suicidal behavior (actual attempt, interrupted attempt, aborted attempt, or preparation towards imminent suicide attempt), or something of equal significance. The development of endometrial hyperplasia with or without atypia would also be consistent with a severe AE.

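### Stage 2 hypertension triggers withdrawal and counts as a severe adverse event, yet the protocol specifies no blood pressure reading after enrolment, so a symptomless rise on drug could go undetected

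*Combined protocol and SAP*

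**What the plan says.** Three places treat raised blood pressure on drug as a safety matter:

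- Section 2.3.1 lists "increased blood pressure" among the less frequent side effects of estradiol.
- Section 7.2, item 3, gives as grounds for withdrawal: "Development of a VTE, breast carcinoma, Stage 2 hypertension, or other medical conditions for which E2 is contraindicated".
- Section 8.3.3.1 includes "an increase in blood pressure consistent with Stage 2 hypertension" among its examples of a severe adverse event.

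Two places specify a measurement, and both concern eligibility:

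- Section 5.2 excludes women with "Stage I or greater hypertension based on 3 stethoscopic measures at enrollment".
- Section 8.2, under the label "Safety Screening prior to randomization", states: "Three stethoscopic blood pressure readings will be measured at enrollment to rule out hypertension".

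Enrolment is at week 0, the first patch at week 8 and the last lab session at week 24 (sections 1.2 and 1.3). No numeric threshold for Stage 2 is given.

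**The concern.** The protocol acts on a blood pressure result that it does not plan to obtain. Stage 2 hypertension is defined by a measurement and can be silent, so asking about side effects would not reliably find it.

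Four actions depend on its being found: withdrawal (section 7.2), consultation within 24 hours of a severe event (section 8.3.4), the report to the IRB and DSMB within one week (section 8.3.5), and inclusion in the six-monthly Fisher exact test of moderate or severe events by arm (sections 7.1 and 9.4.4). These are four consequences of one omission, not four separate faults. If estradiol does raise blood pressure, missed cases would make the arms look more alike in the comparison that the DSMB receives.

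No efficacy endpoint is at stake in the omission itself. A carelessly placed reading could, however, disturb one, and the fix has to allow for that.

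**Working it through.** The plan states no figure to reproduce. The check is a reading of the sections that say what happens at visits, followed by arithmetic on the timeline.

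**What the sections on drug-phase visits name**

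- Section 8.3.4: side effects and adverse events, bleeding, suicide assessment, and STAI-S and SHAPS increases. No blood pressure.
- Section 6.4: patch education, application dates, used and unused patches. No blood pressure.
- Section 8.2, stress test: each step with its duration, and cortisol sampling. No blood pressure.
- Section 10.1.6: the DSMB sees recorded side effects and symptoms, and calls from participants.
- Sections 1.2 and 1.3: no blood pressure entry. The row "Physical and gynecological exam (including height and weight" is marked at week 0 only. This is weaker evidence, because the schedule has no row for the enrolment readings either.

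By contrast, the detection of other withdrawal events is spelled out. Section 8.3.4 gives bleeding checks with ultrasound and biopsy rules for hyperplasia, and clinician assessment at weeks 8, 16, 20 and 24 for suicidality.

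Readings specified on drug: 0.

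**Longest stretch on drug without a reading (weeks 8 to 24)**

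- As written: 24 − 8 = 16 weeks.
- Readings at weeks 16, 20 and 24: max(8, 4, 4) = 8 weeks.
- One more at week 8 + k: max(k, 8 − k, 4) = 7, 6, 5, 4, 5, 6, 7 for k = 1 to 7. Week 12 is best, at 4 weeks.

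**Patch exposure that a confirmed finding could spare**

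The number of weeks left is 24 minus the week of detection: up to 12 at week 12, up to 8 at week 16, up to 4 at week 20 and 0 at week 24. A week 24 reading only completes the event count.

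**Whether weekly visits exist on drug**

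Section 7.2, item 7, refers to weekly visits before and after randomization. Section 8.3.4 has visits weekly at first and then monthly for two months. With sessions at weeks 16, 20 and 24, the weekly phase most naturally covers weeks 8 to 16.

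**Workload**

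Sets = women × sets per woman; hours = sets × minutes ÷ 60. The 5 to 10 minutes per set is an assumption. The number of women is 120 (sections 4.2 and 6.3), 138 (section 9.2) or 250 (synopsis and section 2.1).

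| Women | 4 sets each | Hours | 5 sets each | Hours |
|---|---|---|---|---|
| 120 | 480 | 40 to 80 | 600 | 50 to 100 |
| 138 | 552 | 46 to 92 | 690 | 58 to 115 |
| 250 | 1,000 | 83 to 167 | 1,250 | 104 to 208 |

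**Session time**

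The timed parts in section 8.2 are the stress test, 30 + 5 + 10 + 5 + 5 + 45 = 100 minutes, the Dot Probe, 15, and the EEfRT, 20: 135 minutes in all. Adding 5 to 10 minutes is 3.7% to 7.4% of that. The share of the whole session is smaller, because questionnaires and safety checks have no stated length.

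**The case against.** The strongest objection is that the protocol does not list everything done at a visit. The schedule of activities omits the suicide assessments and bleeding checks as well as the enrolment blood pressure readings. Visit content may sit in the Adverse Events Form (section 10.1.6) or the Manual of Procedures (section 10.1.10). That stands, and it limits the point to what the protocol specifies. A reader might infer that no blood pressure is taken on drug. The documents do not show that.

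Second, venous thromboembolism and breast carcinoma, in the same item of section 7.2, also have no scheduled check on drug. True, and breast disease too can be silent. The remaining distinction is practical: blood pressure can be checked in minutes at visits that already take place.

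Third, harm is probably infrequent. The side effect is listed as less frequent, Stage I or greater hypertension is excluded at entry, exposure is 16 weeks, and side effects are reviewed at visits. This also stands. A reader might infer that cases will be missed, or that the adverse event comparison is materially biased. The documents give no incidence, and the comparison pools all moderate and severe events, so neither follows.

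Fourth, adding readings only after baseline would make follow-up sessions differ from week 8, from which every endpoint's change is measured. Repeats, or talk of a raised reading, could affect the state STAI. If estradiol raises blood pressure, they would fall more often on the active arm and could hint at allocation. This is right, and it determines how the reading should be taken.

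**Conclusion.** The point holds as a gap in the protocol text. A stated withdrawal rule and a named severe adverse event depend on a measurement that the protocol specifies only at enrolment. As written, a symptomless rise to Stage 2 could go undetected through all 16 weeks on drug and be missing from the six-monthly comparison. The number of such cases cannot be derived and is probably low, so this is an inexpensive safety improvement, not evidence of harm or a threat to the efficacy analysis. The conclusion assumes that no document outside those available already requires a reading. If one does, the gap is a missing citation.

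**What to change.** Add a seated resting blood pressure row to the schedule of activities and to section 8.2:

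- at week 8, mandatory and before the first patch;
- at weeks 16, 20 and 24;
- at one weekly on-drug visit between weeks 8 and 16, ideally week 12.

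At all four lab sessions take the reading in the same way, on arrival, before the step described as "Baseline Rest (30 mins): The subject will rest for 30 minutes". It then precedes the baseline cortisol sample by at least 30 minutes. Unless clinically urgent, leave any repeat or discussion of a raised reading until the STAI, stress test and cortisol sampling are finished. Baseline and follow-up sessions then match, and the state STAI and the blind are protected.

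State the Stage 2 threshold, as set by the study clinicians, and require a confirmed repeat before withdrawal. If the Adverse Events Form or Manual of Procedures already requires readings, cite it in section 8.2 instead.

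No new visit is needed. The cost is 4 to 5 reading sets per woman, with the totals tabulated above, and follow-up of some raised readings that will not be confirmed on repeat.
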